- Per Protocol (PP) Set: The Per Protocol Set (PPS) will include all patients who 1) were administered any amount of study medication, and 2) have completed at least 65% of the study dosing visits with or without receiving study drug (eg at least 4 of 6 TP Day 0 visits for patients receiving SEL-212 or at least 8 of 12 TP Day 0 or Day14 visits for patients receiving Krystexxa) unless early termination from the study occurred after study drug withdrawal due to meeting stopping rules or due to an adverse event, or due to PI discretion (for example where at least one pre-dose SUA was >6 mg/dL in the Krystexxa arm and patient was discontinued from study treatment), and 3) who have no major Protocol deviations affecting the primary efficacy assessments. Patients will be analyzed according to randomized treatment.

Efficacy Analyses

Primary Efficacy Analysis

The primary estimand will take into consideration the treatment policy strategy, ie, Treatment Period 6 (and also Treatment Period 3) assessments will be considered for all subjects in ITT independently whether the subject has completed the study treatment or has terminated early the study treatment. Additionally, the estimand based on the while-on-treatment strategy for dealing with study treatment terminators will be defined. For all used estimands of the primary efficacy, the estimator for the comparison between the treatment groups is defined as the difference in the proportion of responders between subjects receiving SEL-212 versus those receiving KRYSTEXXA during Treatment Periods 3 and 6. The statistical testing will be performed confirmatory using the Cochran-Mantel-Haenszel (CMH) test – considering the randomization stratum of tophus presence (yes/no) – with a one-sided type 1 error rate $\alpha = 5\%$. In addition, 90% two-sided confidence intervals for the overall treatment difference between SEL-212 and KRYSTEXXA treatment groups without stratification will be computed. The analysis of the estimands will be carried out based on the ITT primarily. Supportive analyses will be performed on the mITT and the PP. For each defined estimand sensitivity analyses will be performed using different imputation approaches for missing values. Details of the applied approaches will be presented in the Statistical Analysis Plan.

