All statistical tests in secondary endpoints for the comparison between SEL-212 and KRYSTEXXA will be performed using one-sided tests at a type 1 error rate level of $\alpha=5\%$. In addition, 90% confidence intervals for treatment differences between SEL-212 and KRYSTEXXA treatment groups will be computed. The efficacy analyses will be carried out based on the ITT and PP Sets. mITT analyses will be performed if appropriate.

For assessment of SUA in the secondary efficacy analyses, summary tables of the number and percentage of subjects for each endpoint will be presented by treatment group, and the comparison between the treatment groups will be performed similar to the primary efficacy endpoint using a CMH-test considering the randomization stratum.

For the health questionnaires, comparison with regards to change from baseline in health questionnaires will be performed using an ANCOVA with the respective change from baseline value as dependent variable, treatment group and the randomization stratum as

independent fixed factors and the baseline value as independent covariate. For each health questionnaire, summary tables of total scores or domain scores and subscale scores will be provided for each scheduled assessment time by treatment group. Additionally, summaries of the changes from baseline will be provided.

The number and percentage of subjects reporting gout flares per 3-months period, i.e. Treatment Periods 1 to 3 and Treatment Periods 4 to 6, will be summarized by treatment group and will be tested using a CMH-test considering the randomization stratum. The frequency of gout flares will be summarized per 3-months period, i.e. for Treatment Periods 1 to 3 and Treatment Periods 4 to 6 for each treatment and will be compared using ANOVA considering the randomization stratum and treatment as fixed factors.

Comparison with regards to change of tender joints and swollen joints from baseline will be performed using an ANCOVA with the change from baseline value as dependent variable, treatment group and randomization stratum as independent fixed factors and the baseline number of tender joints and swollen joints as independent covariates, respectively. In case of non-normality, the non-parametric Wilcoxon test will be used for the comparison between the treatment groups. Summary tables of the number of tender joints and swollen joints for each assessment timepoint and for the change from baseline will be provided by treatment group, respectively.

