5.4 Impact on Quality of Life

One longitudinal study in this patient population reports that approximately 70% of patients with chronic refractory gout have at least 1 tophus and an average of 7 flares per year. In a separate study of chronic refractory gout, patients self-reported more than 60% of these flares as crippling ([Brook 2010](#)). Symptoms of pain, limited mobility, and disability are debilitating and deeply affect physical function and emotional and social functioning, and disease severity correlates with a marked compromise in quality of life ([Strand 2012](#), [Becker 2009](#)).

The relationship between self-reported quality of life and disability and disease severity have been evaluated in multiple clinical studies. Over 100 subjects with chronic refractory gout evaluated using the Medical Outcomes Study Short Form-36 assessment, and results revealed that patients with chronic refractory gout have significantly lower subscales analogous to those of 75-year old individuals ([Becker 2009](#)). Specifically, disease severity, as characterized by number of flares in the past year, number of tender or swollen joints, or presence of tophi, significantly correlates with worse quality of life scores in all areas, which include bodily pain, general health, mental health, physical functioning and vitality. Subjects with comorbidities

experienced worse physical functioning. Notably, their scores did not improve over the 52-week period despite undergoing maximal medical management (*Strand 2012*).

There is also evidence that gout affects workplace productivity, as studies in patients with chronic, refractory gout self-report work absences due to flares, losing 25.1 workdays on average per year. Another study specifically found employees with gout missed 4.56 more days of work per year than those without gout (*Edwards 2011*).

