3.5. Determination of Sample Size

The primary efficacy criterion in this study is defined as the percentage of patients who achieve and maintain reduction of SUA < 6 mg/dL for at least 80% of the time during Treatment Period 3 and Treatment Period 6. The percentage of responders according to the above criterion is assumed to be 65% in the SEL-212 arm and 44% in the KRYSTEXXA® arm. Using the Chi-square test for comparison between the SEL-212 arm and the KRYSTEXXA® arm, and considering a one-sided $\alpha=5\%$ and the statistical power of 80%, results in 69 patients per treatment group. Taking into account that some patients may be excluded from the mITT analyses, 75 patients per treatment group will be randomized. For the sample size estimation, Chi-square test, instead of the Cochran-Mantel-Haenszel test, is used although the randomization will be stratified for tophus presence (yes/no) as there is no valid assumption of the distribution of this stratification variable within the eligible patient population.

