The estimator for the comparison between the treatment groups is defined as the difference in the proportion of responders between patients receiving SEL-212 versus those receiving KRYSTEXXA® during Treatment Periods 3 and 6. The statistical testing will be performed confirmatory using the Cochran-Mantel-Haenszel (CMH) test – considering the randomization stratum of tophus presence (yes/no) – with a one-sided type 1 error rate $\alpha = 5\%$. In addition, 90% two-sided confidence intervals for the overall treatment difference between SEL-212 and KRYSTEXXA® treatment groups without stratification will be computed. The analysis of the estimands will be carried out based on the ITT primarily. Supportive analyses will be performed on the mITT and the PP.

A logistic regression model to compare treatment difference controlling for presence of tophus will be performed as supportive analysis.

In addition, a sensitivity analysis will be performed as below for the primary endpoint:

- If a subject withdraws from study treatment before completing period 6 due to stopping rules met for treatment, the subject will be considered as a non-responder for the primary efficacy endpoint.
- If a subject withdraws from the study before completing period 6 or the study terminates prior to a subject completing period 6, the primary efficacy endpoint is based on SUA assessment for period 3 where $T1$ be the total time interval in hours for Treatment Period 3 of which $W1$ hours is the time interval during which SUA level is < 6 mg/dL:

$$\text{Percentage (p)} = \frac{W1}{T1} \times 100$$

Summary tables of the percentage of responders (patients who achieve and maintain reduction of SUA < 6 mg/dL for at least 80% of the time) will be provided by treatment group. Additionally, a summary table with the total time a patient has SUA values < 6 mg/dL will be provided for treatment period 3 and treatment period 6 by treatment group.

Summary tables of the actual values and change from baseline for SUA results will be provided for each scheduled sampling time point by treatment group.

This document is confidential.

Additionally, mean SUA level, reduction in mean SUA and percent reduction in mean SUA from baseline during Treatment Periods 3 and 6, during Treatment 3, and during Treatment Period 6 will be summarized by treatment group respectively and will be compared for treatment difference using ANOVA model with presence of tophus and treatment group as fixed factors

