7.2.1. Secondary Efficacy Endpoints based on SUA

For the following secondary endpoints, the comparison between SEL-212 and KRYSTEXXA® will be done similar to the primary efficacy endpoint using a CMH-test considering the randomization stratum of tophus presence (yes/no) with one-sided type 1 error rate level of $\alpha=5\%$. In addition, 90% confidence intervals for treatment differences between SEL-212 and KRYSTEXXA® treatment groups will be computed. The efficacy analyses will be carried out based on the ITT and PP Sets. mITT analyses will be performed as supportive.

- percentage of patients who achieve and maintain reduction of SUA < 6 mg/dL for at least 80% of the time during Treatment Period 3
- percentage of patients who achieve and maintain reduction of SUA < 6 mg/dL for at least 80% of the time during Treatment Period 6
- percentage of patients who achieve and maintain reduction of SUA < 6 mg/dL for 100% of the time during Treatment Period 6
- percent of patients whose pre-dose SUA values > 6 mg/dL during Treatment Periods 2-6

A summary table of the number and percentage of patients who achieve and maintain reduction of SUA < 6 mg/dL for at least 80% of the time during Treatment Period 6 will be provided by treatment group.

A summary table of the number and percentage of patients who achieve and maintain reduction of SUA < 6 mg/dL for at least 80% of the time during Treatment Period 3 will be provided by treatment group.

A summary table of the number and percentage of patients who achieve and maintain reduction of SUA < 6 mg/dL for 100% of the time during Treatment Period 6 will be provided by treatment group.

A summary table of the number and percentage of patients who achieve and maintain reduction of SUA < 6 mg/dL for 100% of the time during Treatment Period 3 will be provided by treatment group.

A summary table of the number and percentage of patients with pre-dose SUA values > 6 mg/dL during Treatment Periods 2-6 will be provided by treatment group.

This document is confidential.

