11.2.5.2. Table Conventions

- Units will be included where available

This document is confidential.

- If the categories of a parameter are ordered, then all categories between the maximum and minimum category are presented in the table, even if n=0 for all treatment groups in a given category that is between the minimum and maximum level for that parameter. For example, the frequency distribution for symptom severity would appear as:

Severity Rating	N
severe	0
moderate	8
mild	3

Where percentages are presented in these tables, zero percentages will not be presented and so counts of 0 will be presented as 0 and not as 0 (0%).

- If the categories are not ordered (e.g., Medical History, Reasons for Discontinuation from the Study, etc.), then only those categories for which there is at least 1 patient represented in 1 or more groups are included.
- An Unknown or Missing category are added to each parameter for which information is not available for 1 or more patients.
- Unless otherwise specified, the estimated mean and median for a set of values are printed out to 1 more significant digit than the original values, and standard deviations are printed out to 2 more significant digits than the original values. The minimum and maximum should report the same significant digits as the original values. For example, for systolic blood pressure:

N	XX
Mean	XXX.X
Std Dev	X.XX
Median	XXX.X
Minimum	XXX
Maximum	XXX

- P-values are output in the format: "0.xxx", where xxx is the value rounded to 3 decimal places. Every p-value less than 0.001 will be presented as <0.001. If the p-value are less than 0.0001, then present as <0.0001. If the p-value is returned as >0.999, then present as >0.999
- Percentage values are printed to one decimal place, in parentheses with no spaces, one space after the count (e.g., 7 (12.8%), 13 (5.4%)). Pre-determine how to display values that round down to 0.0. A common convention is to display as '<0.1', or as appropriate with additional decimal places. Unless otherwise noted, for all percentages, the number of patients in the analysis set for the treatment group who have an observation will be the denominator. Percentages after zero counts should not be displayed and percentages equating to 100% are presented as 100%, without decimal places.

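### The primary responder difference gets only an unstratified 90% interval with no named method, so it need not agree with the tophus-stratified CMH test beside it

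*SAP*

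**What the plan says.** SAP 7.1 defines the estimator as a difference in responder proportions, without saying whether it is crude or weighted over strata. The confirmatory test is CMH, stratified by tophus presence, at one-sided 5%. The next sentence plans that "90% two-sided confidence intervals for the overall treatment difference between SEL-212 and KRYSTEXXA® treatment groups without stratification will be computed". The Protocol Synopsis and Protocol 13.4.1 carry the same sentence. Neither document names a method for the interval.

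The only other tophus-adjusted analysis of the primary endpoint is a supportive logistic regression, for which no interval and no risk difference is specified.

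For the SUA responder secondaries, SAP 7.2.1 follows the primary analysis with a CMH test and states that "90% confidence intervals for treatment differences between SEL-212 and KRYSTEXXA® treatment groups will be computed". The Protocol Synopsis and 13.4.2 agree. Again no method is named, and whether these intervals are stratified is left open.

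On a separate matter, SAP 7.1 says that mean SUA level, reduction and percent reduction "will be compared for treatment difference using ANOVA model with presence of tophus and treatment group as fixed factors". Baseline SUA is not in that model. Changes in questionnaires and joint counts (SAP 7.2.2 to 7.2.6) are adjusted for baseline.

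**The concern.** A 90% two-sided interval is the natural companion to a one-sided 5% test: its lower limit should exceed zero when the test rejects. That link breaks when the test is stratified and the interval is not. It can also break with no tophus effect at all, because some crude intervals use a different variance from the test.

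Near the boundary, the published interval could exclude zero when the primary test has failed, or include zero when it has succeeded. Because the method is unnamed, the reading could also depend on a choice made after the data are seen. That matters more here because the trial is open-label and SAP 2.2 lets the sponsor see primary-endpoint results when the interim analysis is delivered.

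**Working it through.** **Inputs.** Responder rates 65% vs 44%, one-sided alpha 5%, power 80%, 69 per arm required and 75 randomized (Protocol 13.1, SAP 3.5). SAP 3.5 says "there is no valid assumption of the distribution of this stratification variable within the eligible patient population". Two tophus shares were therefore used: 70%, from Protocol 5.4 ("approximately 70% of patients with chronic refractory gout have at least 1 tophus"), and 50%, assumed. The gap in responder rate between tophus strata is assumed, at 0 to 40 points. A second setting, 58% vs 44%, is also assumed. It was used because it lies near the decision boundary, where CMH rejects in only 51% to 58% of trials.

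**The plan's own figure.** n = [1.645·√(2·0.545·0.455) + 0.842·√(0.65·0.35 + 0.44·0.56)]² / 0.21² = (1.158 + 0.579)² / 0.0441 = 68.5, so 69 per arm. This reproduces.

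**Worked conflicts.** In each stratum, with N = n1 + n0 and m responders in total, CMH uses the deviation x1 − n1·m/N and the variance n1·n0·m(N − m)/[N²(N − 1)]. The crude Wald limits are d ± 1.645·√[p1(1 − p1)/75 + p0(1 − p0)/75].

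- *Case A* (SEL-212 vs KRYSTEXXA): tophus 25/52 vs 18/52, no tophus 17/23 vs 14/23. CMH z = (3.5 + 1.5)/√(6.367 + 2.583) = 1.671.
- *Case B*: tophus 30/52 vs 24/52, no tophus 14/23 vs 10/23. CMH z = (3 + 2)/√(6.553 + 2.933) = 1.623.
- *Case C*: tophus 19/52 vs 14/52, no tophus 23/23 vs 19/23. CMH z = (2.5 + 2)/√(5.687 + 0.933) = 1.749.

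Intervals are in percentage points; MN is Miettinen-Nurminen.

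| | CMH p | Crude Wald | Crude Newcombe | Crude MN | Stratified MN |
|---|---|---|---|---|---|
| A | 0.047 | +0.02 to 26.6 | −0.07 to 26.1 | −0.14 to 26.3 | +0.21 to 26.0 |
| B | 0.052 | +0.03 to 26.6 | −0.07 to 26.1 | −0.13 to 26.3 | −0.18 to 26.4 |
| C | 0.040 | −1.3 to 25.3 | −1.4 to 24.8 | −1.5 to 25.0 | +0.7 to 23.2 |

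In A the test succeeds, and the crude interval agrees or not depending on the method. In B the test fails and crude Wald excludes zero. C is a plain conflict, but it needs a tophus gap of about 56 to 63 points.

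**How often.** There were 200,000 simulated trials per setting, 75 per arm, with fixed strata of 52 and 23 per arm (70% tophus). The table gives the percentage of trials in which the lower limit being above zero and CMH p < 0.05 disagree.

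| Rates | Interval | Gap 0 | 10 | 20 | 30 | 40 |
|---|---|---|---|---|---|---|
| 65 vs 44 | Wald | 2.9 | 2.3 | 0.8 | 0.1 | 0.6 |
| | Newcombe | 0.9 | 1.1 | 1.7 | 2.3 | 3.0 |
| | MN | 0.6 | 1.1 | 2.2 | 2.9 | 3.6 |
| 58 vs 44 | Wald | 5.7 | 4.6 | 2.0 | 0.4 | 0.9 |
| | Newcombe | 1.1 | 1.7 | 3.6 | 5.3 | 6.7 |
| | MN | 0.7 | 1.6 | 4.0 | 5.9 | 7.3 |

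At gaps of 0 to 20, essentially every Wald conflict is an interval excluding zero while CMH fails. At gaps of 20 or more, nearly every MN conflict is the reverse. Crude Wald and crude MN disagree with each other in 2.8% to 3.0% of trials at 65 vs 44 and 5.8% to 6.6% at 58 vs 44, whatever the gap.

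**How far from zero.** At gaps up to 20, no conflicting crude limit lies 0.5 points or more from zero. SAP 11.2.5.2 says "Percentage values are printed to one decimal place". If that applies to interval limits, conflicts at least 0.05 points from zero remain visible. At 65 vs 44 and 70% tophus they occur in 1.9/1.3/0.4/0.1/0.6% of trials (Wald) and 0.2/0.6/1.7/2.3/3.0% (MN) over gaps 0 to 40.

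**Coverage and width.** At gaps of 0 to 20, crude Wald covers 90.5% to 91.3% at 65 vs 44 but 88.1% to 88.9% at 44 vs 44, so it is not reliably conservative. Stratified MN covers 89.4% to 90.6% in all fixed-strata settings. At a gap of 20 and 65 vs 44, stratifying saves 0.2 to 0.4 points on a half-width of about 13.

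**Why stratified MN matches CMH.** Take weights w = n1·n0/N. The weighted difference w(x1/n1 − x0/n0) equals x1 − n1·m/N. At zero difference the constrained rate is m/N, so the MN variance with its N/(N − 1) factor is w²·(m/N)(1 − m/N)(1/n1 + 1/n0)·N/(N − 1) = n1·n0·m(N − m)/[N²(N − 1)], which is the CMH variance. Simulated disagreement was 0% in every setting.

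**Mean SUA.** Let sb and sp be the baseline and on-study SDs and r their correlation. Variance relative to ANCOVA is 1/(1 − r²) for the level and (sp² + sb² − 2·r·sb·sp)/[sp²(1 − r²)] for the change. Over assumed sb 1.0 to 1.5, sp 2.5 to 3.5 and r 0 to 0.4, the loss is 0 to 19% for the level and 0 to 36% for the change. Against the better of the two it is at most 9.9%: at sb 1.5, sp 2.5, r 0.3, the level gives 1/0.91 = 1.099 and the change gives 6.25/5.6875 = 1.099. The 36% needs r = 0, where the level model loses nothing. No loss was computed for percent reduction.

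**The case against.** The unstratified interval is a deliberate, pre-specified choice, repeated in the Protocol Synopsis, Protocol 13.4.1 and SAP 7.1. It suits an overall difference in proportions, and its 90% level matches the one-sided 5% alpha. Nothing confirmatory depends on it. At the planned rates, conflicts with CMH reach 3.6% only under an assumed 40-point tophus gap, and stay at 2.9% or below for gaps up to 20. In case B the crude Wald limit of +0.03 would print as 0.0. The larger figures come from 58 vs 44, which the documents do not contain. The mean-SUA point has nothing to do with agreement between test and interval, and its inputs are all assumed.

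Most of this stands as a limit on weight. The crude interval is not an error for the crude difference, the effect is small, and 58 vs 44 must be read as an assumed near-boundary case. It does not remove the two gaps: the method is unnamed, and no planned interval corresponds to the primary test. The logistic model does not supply one. The mean-SUA point is a separate precision suggestion.

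**Conclusion.** The point holds as an optional improvement to reporting. The only interval planned for the primary risk difference is unstratified and unnamed, and it can contradict the stratified CMH test in either direction. At the planned rates and 70% tophus this happens in 0.1% to 3.6% of simulated trials, nearly always with a limit very close to zero. The choice of crude method alone changes the reading in about 3%. Alpha, power, sample size and the confirmatory decision are unaffected. The frequencies rest on assumed tophus effects and, for the tophus share, on a background figure in the Protocol. The worked cases and the identity between stratified MN and CMH do not depend on those assumptions.

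**What to change.** In SAP 7.1 and 7.2.1, report with each CMH test of an SUA responder endpoint a tophus-stratified risk difference with Mantel-Haenszel weights. Give it a 90% stratified Miettinen-Nurminen interval that uses the N/(N − 1) variance factor in each stratum, and state that CMH is run without continuity correction. Keep the crude difference and its interval as supplementary, and name the method. Do this before any primary-endpoint result is released.

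Separately, and only for precision, add baseline SUA as a covariate in the models for reduction and percent reduction in mean SUA.

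The cost is a few sentences and the programming of one interval and one covariate, with no new data, patients or design change. To align the Protocol as well, the sentences to edit are in the Synopsis (primary and secondary analyses), 13.4.1 and 13.4.2, and Protocol 15.3 requires IRB approval of an amendment. Since Protocol 13 lets the SAP identify modifications to the planned analyses and the crude interval is kept, changing the SAP alone may be enough.
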